## 9. Statistical Plan

a. Sample Size Determination

Using G\*Power 3.1.5 and looking at two sample independent t-test for the primary endpoint, in order to detect an effect size of 0.5 between the groups at 90% power and using significance level of 0.05, 86 patients are required in each study group.

b. Statistical Methods

Categorical variables will be reported as count (frequency). Normally distributed continuous variables will be reported as mean  $\pm$  standard deviation and non-normally distributed continuous variables will be reported as median (interquartile range). To determine if there is a difference in the two groups demographic variables a two sample t-test will be used for normally distributed continuous variables, a Mann Whitney Test will be used for non-normally distributed continuous variables, and a Chi-square will be used for categorical variables unless assumptions aren't met then Fishers Exact test will be used. To compare the anxiety levels of the group of individuals randomized to VR and standard procedural education vs. standard procedural education alone an independent two sample t-test will be used. If assumptions aren't met then a Mann Whitney test will be used. To determine if there is a difference in anxiety before and after the use of VR a paired t-test will be used. If assumptions aren't met then a Wilcoxon Signed Rank test will be used. Significance will be assessed at an alpha of 0.05.

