### **c. Study Endpoints**

The primary measure of interest in the present study is patient anxiety, as measured using the State Trait Anxiety Inventory (2, 3).

In all patients, anxiety will be assessed using this tool at baseline (prior to randomization) and again on the day of the procedure, just prior to undergoing catheterization.

The primary outcome of this study is the anxiety level measured just prior to catheterization, which will be compared in the two study groups.

The preparedness tool results will be compared between the two groups as a secondary analysis.

d. Procedures Involved in the Research

**Standard procedural education.** Standard procedural education for all patients undergoing cardiac catheterization at our site formally comes from two sources. First, it is provided verbally by clinical personnel, including physicians and nurses, during routine clinical interactions (i.e. at the time of office visits) and during subsequent phone calls made by the patient to clinical personnel requesting additional procedural information. Second, clinical personnel provide all patients with an information sheet that describes cardiac catheterization (attached as Appendix A; also available online at [www.kramesondemand.com](http://www.kramesondemand.com)).

**Virtual reality.** The VR experience developed for this study will be provided to participants by study personnel using a smartphone (Moto G, Motorola, Schaumburg, Illinois) and a viewer headset (View-Master, Mattel, Segundo, California). This interactive VR experience was filmed using a commercially available camera (360fly 4K, 360FLY, Pittsburgh, Pennsylvania) and developed using proprietary software by Carnevale Interactive (Grand Rapids, Michigan). The VR simulation will allow participants to experience aspects of their procedural day, starting with arrival in the lobby of the catheterization center. The simulation will progress to the catheterization laboratory registration and waiting room, followed by the pre-procedural holding area and finally the procedure room. In each location, the participant will be able to virtually explore the space and have the option of clicking on certain objects of interest, which will trigger an audio description of the object and its purpose.

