**Visit 1 - Baseline.** All participants will be required to meet with study personnel at an offsite locale (Spectrum Health facility whenever possible) prior to the scheduled LHC to conduct the baseline visit. Once informed consent is obtained, study personnel will administer the State Trait Anxiety Inventory (STAI) assessment to all participants.

**Randomization.** Following the completion of the STAI assessment, participants will be randomized in a 1:1 fashion to undergo either VR combined with standard procedural education or to standard procedural education alone. Prior to enrollment of the first participant, Spectrum Health Office of Research Administration statisticians (who are not be study personnel) provided the randomization assignment schema to Cardiovascular Research staff (also not study personnel). Each assignment was placed in an envelope in the order designated by the statisticians' assignment schema. The envelopes were sealed and sequentially numbered from "1" to "200". The envelopes were stored in the research office in the high-density storage area.

Due to the COVID-19 Pandemic, study personnel are now working primarily from home.

In order to maintain the randomization schema as designed as well as reduce the need for staff to go into the hospital to collect randomization envelopes (thereby reducing their risk of exposure), the randomization process will be, for the remainder of the study, via REDCap database. The coordinator attending the enrollment visit will use REDCap to learn the randomization assignment for that participant while in the field, thus maintaining the blind.

For participants randomized to standard procedure education alone, the baseline visit will be complete. Participants will be thanked (and provided a gift card) and remaining study activities will be reviewed.

For participants randomized to VR intervention, the following will occur:

- A baseline wellness self-assessment will be administered (reporting on absence or presence and degree of severity of headache, nausea, dizziness, fatigue and vision abnormalities)
- The participant will be asked to confirm she or he is seated comfortably and study personnel will ensure the chair and participant are free of direct obstruction

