### ***Visit 2 – Procedure Day***

Study personnel will meet participants in their Prep/Recovery room prior to their procedure and the STAI assessment will be administered to all. A Retrospective Wellness questionnaire will be administered to the VR intervention group only in order to assess for any longer-term adverse effects (e.g., headache lasting several hours) of the VR experience. Postprocedure, a patient preparedness survey will be administered to all participants. All participants will again be thanked for their participation, all questions will be answered and their study participation will conclude.

All of the above activities except for standard procedural education will be research related. The average study participation time frame for all participants will be less than 1 month.

The data collected for this study entails the State-Trait Anxiety Inventory results, wellness self-assessments results, preparedness survey results and meta-data results.

e. Data Management

The data collected for this study will comprise of survey results (State-Trait Anxiety Assessment; VR related wellness assessments; and a preparedness assessment) as well as demographic and medical history data (for general reporting purposes). The data will be collected directly from participants using paper tools, where after the responses will be entered into an electronic data capture (EDC) system. The study EDC will be housed on secure Spectrum Health servers and the paper documents will be stored in secure Spectrum Health facilities.

f. Withdrawal of Subjects

Participants may change their minds at any time and choose to withdraw from this study; however, there are no circumstances under which participants would be withdrawn without their consent.

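### The primary comparison leaves out the pre-randomization STAI score that every participant provides; adjusting for it would add precision at almost no cost

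*Combined protocol and SAP*

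**What the plan says.** Section 8c defines the endpoint: "The primary outcome of this study is the anxiety level measured just prior to catheterization, which will be compared in the two study groups". It also sets the measurement times: "In all patients, anxiety will be assessed using this tool at baseline (prior to randomization) and again on the day of the procedure".

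Section 8d confirms the order of events. At Visit 1, "study personnel will administer the State Trait Anxiety Inventory (STAI) assessment to all participants", and the 1:1 randomization follows. On the procedure day participants are met "prior to their procedure and the STAI assessment will be administered to all".

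Section 9b compares the group given VR and education with "standard procedural education alone an independent two sample t-test will be used", or a Mann-Whitney test if assumptions fail. It names no covariate. Its only analysis of an earlier score is separate: "To determine if there is a difference in anxiety before and after the use of VR a paired t-test will be used", with Wilcoxon signed rank as the fallback.

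Section 9a sizes the trial for the unadjusted t-test: effect size 0.5, 90% power, significance level 0.05, 86 per group.

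**The concern.** The trial measures its own primary outcome in every participant before allocation is known, so treatment cannot have affected that score. Such a score is usually the most useful covariate a trial has, and here the randomized comparison does not use it. The paired test does not fill the gap: it looks at change over time around the VR experience, with no control group, and says nothing about the difference between arms.

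What is at stake is precision. The unadjusted test is unbiased under randomization and keeps its type I error. But it leaves in the residual all the variation in procedure-day anxiety that baseline anxiety could explain, and it does not correct the estimate for whatever baseline difference chance produces. This matters most if the true effect is below 0.5 SD. Section 9a gives no raw difference, standard deviation or rationale for that value, so a smaller effect cannot be ruled out.

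**Working it through.** **Inputs from the documents.** n = 86 per arm, effect d = 0.5 SD, alpha 0.05, target power 90% (section 9a); 1:1 allocation (section 8d). Section 9a does not say whether alpha is two-sided. Two-sided reproduces the stated number; a one-sided t-test would need 70 per arm and does not.

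**Assumed input.** The within-arm correlation r between baseline and procedure-day scores is not in the documents. I use 0.1 to 0.7. Low values are plausible because Form Y-1 (Appendix B) asks about present feelings and the two settings differ. Higher values are plausible because the instrument and the person are the same and participation averages under a month (section 8d, Visit 2).

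**Step 1: the plan's own figure.** The noncentrality is d × √(n/2) = 0.5 × √43 = 3.279 on 170 df. Power from the noncentral t is 90.3% at 86 per arm and 89.99% at 85, so 86 reproduces. At d = 0.4, power at 86 per arm is 74.2%. The standard error of the difference is √(2/86) = 0.1525 SD, and the 95% half-width is 1.974 × 0.1525 = 0.301 SD. The effect detectable with 90% power is 0.497 SD.

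**Step 2: ANCOVA.** Adjusting for baseline multiplies the residual SD by √(1 − r²) and costs one degree of freedom (169 df). For r = 0.5 the factor is √0.75 = 0.866, the noncentrality is (0.5/0.866) × √43 = 3.786, and power is 96.4%. The equivalent n per arm for the unadjusted test is 86/(1 − r²).

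| r | Power, d = 0.5 | Power, d = 0.4 | 95% half-width (SD) | Detectable at 90% (SD) | Equivalent n per arm |
|---|---|---|---|---|---|
| unadjusted | 90.3% | 74.2% | 0.301 | 0.497 | 86 |
| 0.1 | 90.6% | 74.6% | 0.300 | 0.495 | 86.9 |
| 0.2 | 91.4% | 75.9% | 0.295 | 0.487 | 89.6 |
| 0.3 | 92.8% | 78.1% | 0.287 | 0.474 | 94.5 |
| 0.5 | 96.4% | 85.3% | 0.261 | 0.431 | 114.7 |
| 0.7 | 99.5% | 95.5% | 0.215 | 0.355 | 168.6 |

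**Step 3: check of the formula.** The formula ignores a variance inflation of about 0.6% from estimating the slope (roughly 1/169). A 20,000-run simulation with normal data includes it. For r = 0.1 / 0.2 / 0.3 / 0.5 / 0.7 it gave:
- ANCOVA power at d = 0.5: 90.5 / 91.3 / 92.6 / 96.4 / 99.5%
- ANCOVA power at d = 0.4: 74.0 / 75.4 / 77.7 / 85.3 / 95.2%
- rejection under the null: 4.9% to 5.2% for ANCOVA and 5.0% to 5.3% for the t-test

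Both tests hold their level. At r = 0.1 and d = 0.4 the simulation shows no gain.

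**Step 4: chance imbalance.** The baseline difference also has standard error 0.1525 SD. A difference of at least 0.2 SD in either direction corresponds to z = 0.2/0.1525 = 1.31, probability 19%. A 0.2 SD imbalance shifts the unadjusted estimate by r × 0.2, that is 0.02 to 0.14 SD, or 4% to 28% of the 0.5 SD design effect. Averaged over randomizations the shift is zero.

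**Step 5: why not a change score.** A change score has SD √(2(1 − r)). At r = 0.3 this is √1.4 = 1.183, and power at d = 0.5 is 78.7%, below the planned test. It is worse than no adjustment whenever r < 0.5, whereas ANCOVA loses at most about one degree of freedom and the small slope-estimation term.

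**The case against.** The strongest reply is that nothing in the plan is wrong. Endpoint, test and sample size agree with one another, the test is valid, and the design power is met. The benefit rests on a correlation nobody has stated. With r between 0.1 and 0.3, power at the design effect rises only to between 90.6% and 92.8%. All of that stands, and it is why this is an improvement and not a correction. It does not argue against the change: if r is low almost nothing is lost, and if r is moderate the interval narrows whatever the true effect is.

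It is also fair to say that imbalance is not a second, separate loss. It is the same explainable variance seen in one particular randomization, and it should not be counted twice.

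A further objection is that the inventory is bounded, the simulation used normal data, and the proposal has no rank-based fallback for the primary analysis. This carries less weight. At 86 per arm ANCOVA needs no stronger distributional assumptions than the planned t-test, and the Mann-Whitney test remains as a sensitivity analysis.

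Finally, the trial is running. Section 8d says "the randomization process will be, for the remainder of the study, via REDCap database", so enrolment had begun at this version. The documents do not show whether outcomes have been looked at by arm, so that condition must be confirmed before the primary analysis is changed.

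**Conclusion.** The point holds as a recommended improvement. The primary comparison omits a baseline score that is already planned for every participant before randomization. The direction of the gain is secure unless r is close to zero. Its size is not known: essentially nil at r = 0.1, modest at 0.3 (half-width 0.301 to 0.287 SD), and substantial at 0.5 to 0.7, where 86 per arm would do the work of about 115 to 169 per arm. The 200-participant enrolment cap in section 8a could not supply those numbers. The figures assume two-sided alpha of 0.05, 86 analysed per arm with both scores present, and a linear relation with equal slopes and approximately normal residuals.

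**What to change.** In section 9b, make the primary analysis an ANCOVA of the procedure-day STAI score on randomized arm, with the baseline score on the same STAI scale as covariate. Report the adjusted mean difference with its 95% confidence interval. Section 8c names no subscale, so the sponsor should confirm which one is primary; if it is the state scale (Form Y-1), use that form for both outcome and covariate. Keep the planned t-test and Mann-Whitney test as sensitivity analyses, and leave the sample size unchanged.

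The cost is one paragraph, with no new data, visits or participants. It does need an amendment, dated and fixed before any outcome data are examined by arm. If that is no longer possible, the t-test should stay primary and the ANCOVA be labelled supportive.

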- The participant will be shown the individual components of the VR system (View-Master with smartphone inserted; external speaker for audio projection; monitor for study staff to observe what the participant is experiencing), be given instructions on how to use the device and encouraged to ask questions.
- Once the participant indicates she or he is ready, they'll be asked to begin the VR experience. Study personnel will stay in the room with the participant for the entire duration and will be viewing on the monitor what the participant is experiencing virtually. Study personnel will provide guidance and answer questions regarding the technology and its use but will not answer questions regarding the facilities, prep, procedure or recovery (this will be explained prior to starting the VR experience).
- When the participant indicates she or he is finished with the VR experience and has had a few minutes to orient, the wellness self-assessment will be administered again.
- Participants will be thanked for their participation (and provided a gift card) and remaining study activities will be reviewed.

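### The paired test of anxiety before and after VR compares baseline with the procedure day in one arm, so it cannot isolate an effect of VR

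*Combined protocol and SAP*

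**What the plan says.** Section 9b lists the paired test directly after the between-arm comparison: "To determine if there is a difference in anxiety before and after the use of VR a paired t-test will be used". A Wilcoxon signed rank test is the fallback, and the section applies an alpha of 0.05 throughout. It names no time points, no analysis set and no control comparator for this test.

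The measurement schedule is in Section 8. Under Study Endpoints (8c): "In all patients, anxiety will be assessed using this tool at baseline (prior to randomization) and again on the day of the procedure". Under Randomization (8d): "Following the completion of the STAI assessment, participants will be randomized in a 1:1 fashion"; the VR session comes after that, in the VR arm only. At the end of the session, once the participant "has had a few minutes to orient, the wellness self-assessment will be administered again", no STAI is given. On the procedure day, participants are met "in their Prep/Recovery room prior to their procedure and the STAI assessment will be administered to all".

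The primary comparison is separate: "The primary outcome of this study is the anxiety level measured just prior to catheterization, which will be compared in the two study groups".

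**The concern.** The wording of the paired test makes VR the event that divides the two measurements. In the schedule, the scores are separated by the whole interval from the baseline visit to the catheterization laboratory. The exact gap is not given; the only guide is in Section 8d, Visit 2: "The average study participation time frame for all participants will be less than 1 month". Over that interval the setting changes and the procedure comes closer. Standard education, including calls made by the patient, may continue. Appendix A says that medicine to relax may be given before the procedure, and its timing relative to the second STAI is not stated. Section 5 itself rests on anxiety in anticipation of the procedure, so a shift with no link to VR is plausible.

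Controls have the same two scores, but this test does not use them. If anxiety rises as the procedure nears, the test can hide a real benefit or make VR look harmful. If anxiety falls for other reasons, VR can be wrongly credited. Either result could be reported at alpha 0.05 beside a valid primary result that it seems to contradict.

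**Working it through.** **Which pair of scores is available.** STAI is taken before randomization and on the procedure day, in both arms (Sections 8c and 8d). The form repeated straight after VR covers headache, vision, nausea, dizziness and fatigue (Appendix C). The preparedness survey is given after the procedure and does not measure anxiety. The only possible pair is therefore baseline STAI and procedure-day STAI. Section 9b names no arm, but use of VR fits only the VR arm.

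**The plan's own figure.** Section 9a gives an effect size of 0.5, 90% power and alpha 0.05. The exact two-sided t-test calculation gives 85.03, rounded up to 86 per group, with power 0.903 at 86. The stated figure reproduces.

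**Assumptions not in the documents.** A natural shift between visits of 0.1 to 0.5 SD, common to both arms; a correlation r between the two scores of 0.3, 0.5 or 0.7; the same SD at both visits.

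**Smallest observed change that reaches p < 0.05.** The SD of a change, in units of the score SD, is sqrt(2(1 − r)). The threshold is t(0.975, 85) × sqrt(2(1 − r)) / sqrt(86), which gives 0.254, 0.214 and 0.166 SD for r = 0.3, 0.5 and 0.7. Relative to the design effect of 0.5, that runs from 0.166/0.5 = 0.33 to 0.254/0.5 = 0.51.

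**No VR effect, natural shift only.** The standardized change is shift / sqrt(2(1 − r)), and the noncentrality is that value times sqrt(86), with 85 df. For example, at r = 0.5 and shift 0.3 the standardized change is 0.3 / 1 = 0.3 and the power is 0.785.

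| Natural shift (SD) | r = 0.3 | r = 0.5 | r = 0.7 |
|---|---|---|---|
| 0 | 0.05 | 0.05 | 0.05 |
| 0.1 | 0.121 | 0.150 | 0.220 |
| 0.2 | 0.341 | 0.450 | 0.658 |
| 0.3 | 0.642 | 0.785 | 0.944 |
| 0.5 | 0.972 | 0.996 | 1.000 |

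Entries are probabilities that the VR-arm paired test is significant. A shift common to both arms cancels in the between-arm comparison. In simulation with a 0.3 SD shared shift (10,000 trials per scenario), the between-arm t-test rejected in 4.9% to 5.3% of trials.

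**Real VR benefit of 0.5 SD, natural rise in both arms.**
- Rise 0.5: the expected change in the VR arm is 0.5 − 0.5 = 0, so the paired test is significant in 5% of trials. The between-arm t-test keeps power 0.903.
- Rise 0.7: the VR arm shows a net rise of 0.7 − 0.5 = 0.2 SD, significant in 34%, 45% or 66% of trials for r = 0.3, 0.5 or 0.7. VR would look harmful although it helps.

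**Between-arm alternatives at 86 per arm, effect 0.5.** ANCOVA uses an effective size of 0.5 / sqrt(1 − r²) with 169 df; the change-score t-test uses 0.5 / sqrt(2(1 − r)).

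| Analysis | r = 0.3 | r = 0.5 | r = 0.7 |
|---|---|---|---|
| Unadjusted t-test (planned) | 0.903 | 0.903 | 0.903 |
| Change-score t-test | 0.787 | 0.903 | 0.988 |
| ANCOVA on baseline STAI | 0.928 | 0.964 | 0.995 |

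**The case against.** The plan asks only whether anxiety differs between two times, and a paired t-test answers that validly. It claims no effect of VR, so the significant results above are true changes, and they become errors only if attributed to VR. The causal question has its own randomized comparison, on which the trial is sized. The paired test belongs to no stated objective or endpoint. All of this is correct, and it limits the harm to one supporting analysis and how it is read. It does not remove the problem: the test carries VR in its wording, sits next to the primary test at the same alpha, and is not labelled descriptive.

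The percentages are also hypothetical. If the procedure-day SD were 1.3 times the baseline SD (again an assumption), a shift of 0.3 baseline SD would give 51%, 65% and 84% instead of 64%, 79% and 94%. The direction of the argument is unchanged.

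Finally, relabelling alone would cure the misreading, and ANCOVA addresses the efficiency of the between-arm analysis. That is fair. ANCOVA is still worth adding, because it answers the question about VR that the paired test appears to ask, using a baseline score that has no stated role in the between-arm anxiety comparison.

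**Conclusion.** The concern holds and should be fixed. That the paired test can only measure a one-arm change from before randomization to the procedure day follows from the visit schedule and needs no assumption. The size of the possible error does rest on assumptions: with equal SDs and r from 0.3 to 0.7, a natural shift of 0.3 SD gives a significant paired result in 64% to 94% of trials when VR does nothing, and a natural rise equal to a 0.5 SD benefit hides that benefit in 95% of trials. The primary between-arm comparison and the sample size of 86 per group are not affected.

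**What to change.** - In Section 9b, remove the VR-arm paired t-test and its Wilcoxon fallback as inference about VR.
- Add a supportive between-arm comparison of the procedure-day STAI adjusted for baseline STAI (ANCOVA). This is a new specification, because the current primary analysis is an unadjusted t-test. State that both scores are the state scale (Form Y-1), since Appendix B contains both the state and trait forms.
- Do not substitute a plain t-test of change scores between arms: it loses power when r is below 0.5 (79% at r = 0.3).
- Report change from baseline to procedure day for both arms side by side, as mean with 95% CI, labelled descriptive.
- The Randomization text in Section 8d shows that enrolment is under way, so date the change and fix it before outcome data are examined by arm.

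The cost is a short amendment and one extra model. No visits, data or participants are added, because both scores are already collected in everyone. Under the assumptions above, ANCOVA has 93%, 96% and 99.5% power for r = 0.3, 0.5 and 0.7, against 90% for the unadjusted test.
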